#### **11.4. Criteria to Permanently Discontinue Treatment**

Treatment with nivolumab, ipilimumab, and/or relatlimab (BMS-986016) should be permanently discontinued for the following:

- Any Grade 2 drug-related uveitis or eye pain or blurred vision that does not respond to topical therapy and does not improve to Grade 1 severity within the re-treatment period OR requires systemic treatment.
- Any Grade 3 non-skin, drug-related adverse event lasting > 7 days, with the following exceptions for drug-related laboratory abnormalities, endocrinopathies, uveitis, pneumonitis, bronchospasm, diarrhea, colitis, neurologic toxicity, hypersensitivity reactions, and infusion reactions:
  - Grade 3 drug-related uveitis, pneumonitis, bronchospasm, diarrhea, colitis, neurologic toxicity, hypersensitivity reaction, or infusion reaction of any duration **requires** discontinuation.
  - For Grade 3 endocrinopathy adverse events such as adrenal insufficiency, ACTH deficiency, hyper- or hypothyroidism, or glucose intolerance, which resolve or are adequately controlled with physiologic hormone replacement (steroids, thyroid hormones) or glucose controlling agents, respectively, **do not require** treatment discontinuation.
  - Grade 3 drug-related laboratory abnormalities **do not require** treatment discontinuation **except**:
    - Grade 3 drug-related thrombocytopenia > 7 days or associated with bleeding **requires** discontinuation.
    - Any drug-related liver function test (LFT) abnormality that meets the following criteria **requires** discontinuation:
      - AST or ALT > 5 x ULN.
      - Total bilirubin > 3 x ULN.
      - Concurrent AST or ALT > 3 x ULN and total bilirubin > 2 x ULN.
- Any Grade 3 myocarditis.
- Any Grade 4 drug-related adverse event or laboratory abnormality, **except for the following events** which do not require discontinuation:
  - Grade 4 amylase or lipase abnormalities that are not associated with symptoms or clinical manifestations of pancreatitis. It is recommended to consult with the sponsor-investigator for Grade 4 amylase or lipase abnormalities.
  - Isolated Grade 4 electrolyte imbalances/abnormalities that are not associated with clinical sequelae and are corrected with supplementation/appropriate management within 72 hours of their onset.
- Any dosing interruption lasting > 6 weeks from the last dose **with the following exceptions**:
  - Dosing interruptions to allow for prolonged steroid tapers to manage drug-related adverse events are allowed. Prior to re-initiating treatment in a subject with a dosing interruption lasting > 6 weeks from the last dose, the sponsor-investigator must be consulted in writing. Tumor imaging assessments should continue as per protocol even if dosing is interrupted.

---

- Dosing interruptions > 6 weeks from the last dose that occur for non-drug-related reasons may be allowed if approved by the sponsor-investigator. Prior to re-initiating treatment in a subject with a dosing interruption lasting > 6 weeks from the last dose, the sponsor-investigator must be consulted. Tumor imaging assessments should continue as per protocol even if dosing is interrupted.

Any adverse event, laboratory abnormality, or intercurrent illness which, in the judgment of the Investigator, presents a substantial clinical risk to the patient with continued study drug dosing should discontinue the study drugs.

The consideration to re-initiate study therapy in selected cases at any time point after discontinuation could be made on a case-by-case basis after considering the overall benefit/risk profile and in consultation between the investigator and the sponsor-investigator. The selected patients will need to meet eligibility criteria. The original dose and schedule and protocol rules would apply accordingly ([Section 11.4](#)).

In this trial, combinatorial treatment with relatlimab and nivolumab (Arm A) or ipilimumab and nivolumab (Arm B) shall be considered separable (see also [Section 9.9](#)):

- **Arm A:** The assessment for discontinuation of drug should be made separately considering each drug component in the nivolumab + relatlimab combination (Arm A). If discontinuation criteria are attributed to only one drug used in this combination, once the patient meets criteria to resume therapy, the subject may continue dosing with nivolumab (if nivolumab was not attributed to criteria for discontinuation) and/or with relatlimab (if relatlimab was not attributed to criteria for discontinuation).
- **Arm B:** The assessment for discontinuation of drug should be made separately considering each drug component in the nivolumab + ipilimumab combination (Arm B). If discontinuation criteria are attributed to only one drug used in this combination, once the patient meets criteria to resume therapy, the subject may continue dosing with nivolumab (if nivolumab was not attributed to criteria for discontinuation) and/or with ipilimumab (if ipilimumab was not attributed to criteria for discontinuation).

If a patient meets criteria for discontinuation and the investigator is unable to determine whether the event is related to both or one study drug, the patient should discontinue all study drugs and be taken off the treatment phase of the study.

## **11.5. Treatment of Nivolumab, Ipilimumab, and Relatlimab Related Infusion Reactions**

If infusion reaction or hypersensitivity were to occur, manifestation might include fever, chills, rigors, headache, rash, pruritus, arthralgias, hypo- or hypertension, bronchospasm, or other symptoms.

According to the relatlimab investigator brochure, the all-combination group of study CA224020 includes 1166 subjects treated with relatlimab and nivolumab. The all-combination group includes Parts B+C+D. In combination therapy (Parts B, C, and D), 22 Grade 1 and 37 Grade 2 infusion-related reactions were reported. There were no Grade 3 or higher infusion reactions reported. The overall frequency (5.1%) observed in Study CA224020 is similar to the frequency observed for nivolumab monotherapy: In patients receiving nivolumab as a 60-minute intravenous infusion, infusion-related reactions occurred in 6.4% (127/1994) of patients; and in a trial assessing the pharmacokinetics and safety of a more rapid infusion, in which patients received nivolumab as a 60-minute intravenous infusion or a 30-minute intravenous infusion, infusion-related reactions occurred in 2.2% (8/368) and 2.7% (10/369) of patients, respectively. Refer to Section 5.9 of the

---

nivolumab label for further details. All events were manageable per updated protocol guidelines, and only 2 subjects required treatment discontinuation, in each case due to recurrent Grade 2 infusion related reactions.

Data regarding serious adverse reactions (i.e. "Serious Adverse Reactions for relatlimab monotherapy and relatlimab + nivolumab Considered Expected for Safety Reporting Purposes (N=1401)" in Table 1-2 of Appendix 1 of the relatlimab investigator brochure lists (serious) infusion related reaction as an uncommon event [i.e. n=4 (0.29%)] with no occurrence of life-threatening or fatal serious adverse reactions.

All Grade 3 or 4 infusion reactions should be reported within 24 hours to the Coordinating Center and reported as an SAE if criteria are met ([Section 13](#)). Infusion reactions should be graded according to NCI CTCAE (version 5.0) guidelines.

Treatment recommendations are provided below and may be modified based on local treatment standards and guidelines as appropriate:

**For Grade 1 symptoms** (Mild reaction; infusion interruption not indicated; intervention not indicated):

- Remain at bedside and monitor subject until recovery from symptoms.
- The following prophylactic premedications are recommended for future infusions: diphenhydramine 50 mg (or equivalent) and/or paracetamol 325 to 1000 mg (acetaminophen) at least 30 minutes before additional nivolumab administrations.

**For Grade 2 symptoms** (Moderate reaction requires therapy or infusion interruption but responds promptly to symptomatic treatment [eg, antihistamines, non-steroidal anti-inflammatory drugs, narcotics, corticosteroids, bronchodilators, IV fluids]; prophylactic medications indicated for ≤ 24 hours):

- Stop the study drug infusion, begin an IV infusion of normal saline, and treat the subject with diphenhydramine 50 mg IV (or equivalent) and/or paracetamol 325 to 1000 mg (acetaminophen); remain at bedside and monitor subject until resolution of symptoms. Corticosteroid or bronchodilator therapy may also be administered as appropriate.
- If the infusion is interrupted, then restart the infusion at 50% of the original infusion rate when symptoms resolve; if no further complications ensue after 30 minutes, the rate may be increased to 100% of the original infusion rate. Monitor subject closely. If symptoms recur then no further study drug will be administered at that visit. Administer diphenhydramine 50 mg IV, and remain at bedside and monitor the subject until resolution of symptoms. The amount of study drug infused must be recorded on the electronic case report form (eCRF).
- The following prophylactic premedications are recommended for future infusions: diphenhydramine 50 mg (or equivalent) and/or paracetamol 325 to 1000 mg (acetaminophen) should be administered at least 30 minutes before additional study drug administrations. If necessary, corticosteroids (recommended dose: up to 25 mg of IV hydrocortisone or equivalent) may be used.

**For Grade 3 or Grade 4 symptoms** (Severe reaction, Grade 3: prolonged [ie, not rapidly responsive to symptomatic medication and/or brief interruption of infusion]; recurrence of symptoms following initial improvement; hospitalization indicated for other clinical sequelae [eg, renal impairment, pulmonary infiltrates]). Grade 4: (life-threatening; pressor or ventilator support indicated):

- Immediately discontinue infusion of study drug.

- Begin an IV infusion of normal saline, and treat the subject as follows. Recommend bronchodilators, epinephrine 0.2 to 1 mg of a 1:1,000 solution for subcutaneous administration or 0.1 to 0.25 mg of a 1:10,000 solution injected slowly for IV administration, and/or diphenhydramine 50 mg IV with methylprednisolone 100 mg IV (or equivalent), as needed.
- Subject should be monitored until the investigator is comfortable that the symptoms will not recur.
- Study drug will be permanently discontinued.
- Investigators should follow their institutional guidelines for the treatment of anaphylaxis. Remain at bedside and monitor subject until recovery from symptoms.
- In the case of late-occurring hypersensitivity symptoms (eg, appearance of a localized or generalized pruritus within 1 week after treatment), symptomatic treatment may be given (eg, oral antihistamine, or corticosteroids).

## **11.6. Management Algorithms for Immuno-Oncology Agents**

Immuno-oncology (I-O) agents are associated with adverse events (AEs) which in severity and duration can differ from AEs caused by other therapeutic classes. In this protocol, nivolumab, ipilimumab, and relatlimab are considered immuno-oncology agents. Early recognition and management of AEs associated with immuno-oncology agents may mitigate severe toxicity.

Management Algorithms have been developed to assist investigators in assessing and managing the following groups of AEs:

- Gastrointestinal
- Renal
- Pulmonary
- Hepatic
- Endocrinopathy
- Skin
- Neurological
- Myocarditis.

For the above events deemed by the investigator as possibly, probably or definitely related to nivolumab, ipilimumab, and/or relatlimab, Management Algorithms are found in [Appendix 6](#).

While safety management algorithms for similar adverse events may be presented elsewhere (e.g. ipilimumab investigator brochure), the recommendations for the combinatorial treatments outlined in this study protocol are to follow the nivolumab-based algorithms for immuno-oncology agents, in order to standardize safety management in this protocol. For individual cases, adverse event treatment management algorithms included in the nivolumab IB or ipilimumab IB might be considered.

The guidance provided in these algorithms should not replace the investigator's medical judgment but should complement it.

## **12. DRUG FORMULATION, SUPPLY AND STORAGE**

### **12.1. Description of Nivolumab**

Nivolumab (OPDIVO) is a programmed death receptor-1 (PD-1) blocking antibody that is currently approved for a variety of indications including melanoma with lymph node involvement or metastatic disease after complete resection, in the adjuvant setting; unresectable or metastatic melanoma, as a single agent or in combination with ipilimumab; metastatic non-small cell lung cancer and progression on or after platinum-based chemotherapy; metastatic small cell lung cancer with progression after platinum-based chemotherapy and at least one other line of therapy; advanced renal cell carcinoma after prior anti-angiogenic therapy; intermediate or poor risk, previously untreated advanced renal cell carcinoma, in combination with ipilimumab; classical Hodgkin lymphoma that has relapsed or progressed after autologous hematopoietic stem cell transplantation (HSCT) and brentuximab vedotin, or 3 or more lines of systemic therapy that includes HSCT; recurrent or metastatic squamous cell carcinoma of the head and neck with progression on or after platinum-based therapy; locally advanced or metastatic urothelial carcinoma with progression (during or following platinum-containing chemotherapy, or within 12 months of neoadjuvant or adjuvant treatment with platinum-containing chemotherapy); adult and pediatric metastatic colorectal cancer (microsatellite instability-high or mismatch repair deficient) after progression on a fluoropyrimidine, oxaliplatin, and irinotecan, as a single agent or in combination with ipilimumab; and hepatocellular carcinoma after sorafenib treatment.

### **12.2. Packaging of Nivolumab**

The study will supply nivolumab to the site.

Nivolumab is typically available as nivolumab injection: 40 mg/4 mL (10 mg/mL), 100 mg/10 mL (10 mg/mL), and 240 mg/24mL (10 mg/mL) clear to opalescent, colorless to pale-yellow solution in a single-dose vial.

Nivolumab drug product should be visually inspected for particulate matter and discoloration prior to administration. Discard the vial if the solution is cloudy, discolored, or contains extraneous particulate matter other than a few translucent-to-white, proteinaceous particles. Do not shake the vial.

### **12.3. Handling and Storage of Nivolumab**

Nivolumab product does not contain a preservative. Nivolumab will be prepared according to the product label. After preparation, the diluted nivolumab solution should be stored either:

- At room temperature for no more than 8 hours from the time of preparation to end of the infusion. Discard diluted solution if not used within 8 hours from the time of preparation; or
- Under refrigeration at 2°C to 8°C (36°F to 46°F) for no more than 24 hours from the time of preparation to end of infusion. Discard diluted solution if not used within 24 hours from the time of preparation.

Do not freeze.

#### **12.4. Description of Ipilimumab**

Ipilimumab (YERVOY) is a recombinant human monoclonal antibody that binds to the cytotoxic T-lymphocyte-associated-antigen 4 (CTLA-4), a negative regulator of T-cell activity. An IgG1 kappa immunoglobulin, ipilimumab is approved for treatment of unresectable or metastatic melanoma; adjuvant treatment of cutaneous melanoma with involvement of regional lymph nodes after resection; intermediate or poor risk, previously untreated advanced renal cell carcinoma, in combination with nivolumab; and under accelerated approval for microsatellite instability-high (MSI-H) or mismatch repair deficient (dMMR) metastatic colorectal cancer that has progressed following treatment with a fluoropyrimidine, oxaliplatin, and irinotecan, in combination with nivolumab.

#### **12.5. Packaging of Ipilimumab**

The study will provide ipilimumab to the site.

Ipilimumab is a sterile, preservative-free, clear to slightly opalescent, colorless to pale yellow solution for intravenous infusion, which may contain a small amount of visible translucent-to-white, amorphous ipilimumab particulates. It is typically supplied in single-use vials of 50 mg/10 mL (5 mg/mL) and 200 mg/40 mL (5 mg/mL). Each milliliter contains 5 mg of ipilimumab and the following inactive ingredients: diethylene triamine pentaacetic acid (DTPA) (0.04 mg), mannitol (10 mg), polysorbate 80 (vegetable origin) (0.1 mg), sodium chloride (5.85 mg), tris hydrochloride (3.15 mg), and water for injection, USP at a pH of 7.

#### **12.6. Handling and Storage of Ipilimumab**

Store ipilimumab under refrigeration at 2°C to 8°C (36°F to 46°F). Protect ipilimumab from light by storing in the original carton until time of use. Do not freeze or shake.

#### **12.7. Description of Relatlimab (BMS-986016)**

Relatlimab (also known as BMS-986016) is a fully human antibody against the lymphocyte activation gene 3 (LAG-3) product. LAG-3 (CD223) is a negative regulatory T-cell receptor implicated in the control of T-cell function in conventional and regulatory T cells. An immunoglobulin G4 (IgG4) isotype antibody including a stabilizing hinge mutation (S228P), relatlimab binds to the LAG-3 receptor on T cells with high affinity, thus blocking LAG-3 interactions with its ligand, the major histocompatibility complex (MHC) Class II, the peptide antigen presentation molecule recognized by CD4+ T-cells. When administered alone or in combination with other therapeutic immuno-oncology monoclonal antibodies, it is hoped that relatlimab may enhance the anti-tumor immune response via blocking the downregulatory pathway otherwise involved in maintaining T-cell quiescence.

#### **12.8. Packaging of Relatlimab**

The study will supply to each site relatlimab injection drug product for intravenous (IV) administration.

Two formulations of relatlimab injection for IV administration are currently available as 100 mg/vial (10 mg/mL) in 10-cc vials. The same excipients are used for both formulations, except for one formulation with and the other without pentetic acid. A third relatlimab formulation (with pentetic acid) for IV administration is also currently available as 80mg/vial.

All three relatlimab formulations for IV administration are a colorless to pale yellow liquid, clear to

slightly opalescent, and light (few) particles (consistent in appearance to protein particulates) may be present. All three formulations are pH 5.0 to 6.0, with a container closure system of a 10cc Type 1 flint glass vial stoppered with fluoropolymer film-laminate rubber stoppers and sealed with aluminum seals. The components of the 3 relatlimab formulations for IV administration are:

- Relatlimab injection (100mg/vial) without pentetic acid: Relatlimab, histidine, histidine hydrochloride monohydrate, sucrose, polysorbate 80, water for injection.
- Relatlimab injection (100mg/vial or 80mg/vial) with pentetic acid: Relatlimab, histidine, histidine hydrochloride monohydrate, sucrose, pentetic acid, polysorbate 80, water for injection.

Note: In addition to the three relatlimab formulations for IV administration mentioned above, two additional relatlimab products are also available for subcutaneous administration (e.g. see Table 3.2.1-1 of the investigator brochure). However, under this clinical study protocol as presently configured, there are no current plans for subcutaneous administration of relatlimab (which will continue to be administered as an intravenous infusion consistent with above protocol Section 9).

### **12.9. Handling and Storage of Relatlimab**

Relatlimab drug product for intravenous administration should be stored at 2°C to 8°C (36°F to 46°F) with protection from light. Do not freeze the drug product.

The intravenous administration of relatlimab infusion must be completed within 24 hours of preparation. If not used immediately, the infusion solution may be stored in a refrigerator at 2°C to 8°C (36°F to 46°F) for up to 24 hours and a maximum of 4 hours of the total 24 hours can be at room temperature (15°C to 25°C; 59°F to 77°F) and exposed to room light. The maximum 4-hour period under room temperature and room light conditions includes the product administration period.

### **12.10. Relatlimab Drug Accountability and Compliance Check**

The investigator is responsible for ensuring accountability for relatlimab, including maintenance of drug accountability records.

Drug accountability records will appropriately document a full inventory relatlimab including:

- Confirmation of relatlimab delivery to the trial site
- A record of each dose of relatlimab dispensed
- The return of relatlimab provided by the study to the sponsor-investigator or designee, or documentation of destruction at the site (if drug destruction at the site is authorized in advance in writing by the sponsor-investigator or designee).

Records will specify relevant dates, quantities, batch numbers, use-by dates and patient numbers, as applicable.

The investigator, or designee, should maintain records that adequately document:

- That patients were provided the doses specified by the clinical trial protocol, and
- That all relatlimab provided by the study was fully reconciled.

## **13. SAFETY REPORTING OF ADVERSE EVENTS**

### **13.1. General**

Adverse events will be graded according to the NCI's Common Terminology Criteria for Adverse Events (NCI CTCAE), Version 5.0, dated November 27, 2017, currently locatable via the following URL:

<[https://ctep.cancer.gov/protocoldevelopment/electronic\\_applications/docs/CTCAE\\_v5\\_Quick\\_Reference\\_8.5x11.pdf](https://ctep.cancer.gov/protocoldevelopment/electronic_applications/docs/CTCAE_v5_Quick_Reference_8.5x11.pdf)>.

If events are not listed in the CTCAE, severity may be designated as mild, moderate, severe, life-threatening, or fatal which respectively correspond to Grades 1, 2, 3, 4, and 5 on the NCI CTCAE, with the following definitions:

- **Mild:** Asymptomatic or mild symptoms; clinical or diagnostic observations only; intervention not indicated;
- **Moderate:** Minimal, local or noninvasive intervention indicated; limiting age-appropriate instrumental activities of daily living (ADL) such as preparing meals, shopping for groceries or clothes, using the telephone, managing money, etc;
- **Severe:** Medically significant but not immediately life-threatening; hospitalization or prolongation of hospitalization indicated; disabling; limiting self care ADL such as bathing, dressing and undressing, feeding self, using the toilet, taking medications;
- **Life-threatening:** Urgent intervention indicated to prevent risk of death present at the time of the event;
- **Fatal:** An event that results in the death of the patient.

Information on adverse events, whether serious or not, whether reported by the participant, directly observed, or detected by physical examination, laboratory test or other means, will be collected, recorded, followed and reported as described in the following sections.

Non-serious adverse events experienced by a participant will be collected and reported from initiation of nivolumab/relatlimab/ipilimumab, throughout the study; and until 100 days after patient's final study-indicated treatment with nivolumab, relatlimab or ipilimumab (whichever occurs last) or until initiation of another anticancer therapy – whichever occurs first. Participants who experience an ongoing adverse event possibly, probably or definitely related to a study procedure and/or study medication beyond 100 days will continue to be contacted by a member of the study team until the event is resolved, stabilized, or determined to be irreversible or not clinically significant by the investigator.

After informed consent but prior to initiation of nivolumab/relatlimab or nivolumab/ipilimumab, non-serious adverse events should be reported only if possibly, probably or definitely attributed by the patient's study physician to a protocol-mandated procedure or intervention.

**After informed consent, any Serious Adverse Event (SAE) that occurs during the clinical study or within 100 days after a patient's last dose of protocol-indicated nivolumab, relatlimab or ipilimumab, regardless of causality to study drug, must be reported to the Coordinating Center in an expedited fashion as directed below (Reporting Procedures).**

During the 30-day follow-up period, new onset, non-serious adverse events should only be recorded if, in the opinion of the investigator, there is a reasonable possibility the event is attributable to the investigational product. Non-serious adverse events related to the next phase of the patient's treatment should NOT be recorded. All serious adverse events occurring within

---

the 30-day follow-up period must be reported, regardless of suspected causality.

Participants should be instructed to report any serious post-study event(s) that might reasonably be related to participation in this study. The investigator should notify the IRB and the Coordinating Center of any unanticipated death or adverse event occurring after a participant has discontinued or terminated study participation that may reasonably be related to the study.

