Single agent studies using relatlimab (CA224020 and CA224022) demonstrated partial responses in non-small cell lung cancer and marginal zone lymphoma, with numerous other patients showing stable disease. Relatlimab in combination with nivolumab has shown the capacity to induce responses in previously heavily treated advanced solid tumors, with the added ability to trigger responses in tumors that have demonstrated resistance to nivolumab therapy. As of the cutoff date of 15-Jun-2017 for Part B of Study CA224020, in subjects treated with relatlimab and nivolumab combination therapy, partial responses were seen in subjects with melanoma, cervical cancer, NSCLC, and squamous cell carcinoma of the head and neck (SCCHN). As of the cutoff date of 07-Apr-2017 for Study CA224022 in subjects treated with relatlimab and nivolumab combination therapy, partial responses have been seen in subjects with relapsed/refractory Hodgkin lymphoma, with stable disease observed in 1 subject for 6 months (and treatment was continuing). In subjects with melanoma treated with relatlimab and nivolumab combination therapy in Part C of Study CA224020, the overall objective response rate (ORR) was 11.5% (7/61, response evaluable) with a disease control rate of 49%. Biomarker analyses suggested that

subjects whose TIL expressed more LAG-3 had a higher response rate, with a greater than 3-fold increase in ORR observed in subjects with evidence of LAG-3 expression in at least 1% of nucleated cells within the tumor margin, compared to less than 1% LAG-3 expression (18.2% [6/33] and 5.0% [1/20], respectively). PD-L1 expression did not appear to enrich for response.

The safety profile of nivolumab + relatlimab has been largely similar to nivolumab monotherapy. LAG-3 knockout in mice has minimal effects, but combination PD-1 and LAG-3 knockout leads to multiorgan autoimmunity. This result has not been recapitulated in humans. Overall, among 304 patients treated with this combination, 157 (51.6%) had at least one treatment related event, most commonly fatigue (12.2%), diarrhea (6.6%; grade 3 in 1%), pruritus (6.9%), and infusion reaction (5.9%). One patient had a grade 5 event (myocarditis); 10.2% had grade 3-4 toxicities.

**TABLE 2: Summary of Adverse Events Reported in At Least 5% of Subjects During Combination Therapy in Study CA224020, Parts B and C (N = 304)**

Preferred Term	All AEs (Regardless of Causality)			Drug-related AEs		

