## **13.8. Definitions**

### **13.8.1 Adverse Event (AE)**

An adverse event is any undesirable sign, symptom or medical condition or experience that develops or worsens in severity after starting the first dose of study treatment or any procedure specified in the protocol, even if the event is not considered to be related to the study.

Abnormal laboratory values or diagnostic test results constitute adverse events only if they induce clinical signs or symptoms or require treatment or further diagnostic tests.

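### Section 13.1 gives two conflicting rules for recording new-onset, non-serious adverse events in the 30-day follow-up period, and nothing in the protocol says which prevails

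*Combined protocol and SAP*

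**What the plan says.** Section 13.1 contains both rules.

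- **The 100-day rule.** "Non-serious adverse events experienced by a participant will be collected and reported from initiation of nivolumab/relatlimab/ipilimumab, throughout the study", and onward to 100 days after the final dose of whichever study drug is given last, "or until initiation of another anticancer therapy" if that comes first. No causality condition is attached.
- **The 30-day rule.** "During the 30-day follow-up period, new onset, non-serious adverse events should only be recorded if", in the investigator's opinion, there is a reasonable possibility that the product caused them. The next sentence excludes non-serious events that belong to the patient's next treatment.

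Two other statements bear on how these should be read. For the period between consent and first dose, Section 13.1 states a causality filter outright: "non-serious adverse events should be reported only if possibly, probably or definitely attributed by the patient's study physician to a protocol-mandated procedure or intervention". Section 13.8.1 defines an adverse event as one that counts "even if the event is not considered to be related to the study".

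Adverse events are a secondary endpoint (Section 4). The follow-up calendar (Section 7.4) and Section 7.16 schedule adverse event review at the 30-day visit (days 30-37) and the 100-day visit (days 100-114). Section 7.4 also schedules it at end of treatment.

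**The concern.** The two rules give opposite instructions for the same event. A site that follows the 100-day rule enters a new, non-serious, unrelated event in the 30-day follow-up period. A site that follows the 30-day rule leaves it out. The trial runs at the coordinating center and about two further centers, so different sites may follow different paragraphs.

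What is at stake is the all-causality part of the safety data just after treatment stops. The study is open-label, and under the 30-day rule the investigator's opinion on cause decides whether an event enters the database at all. An event left out on that judgment cannot be re-attributed later if a pattern emerges. Non-serious does not mean mild either: Section 13.8.2 defines seriousness separately from the severity grades in Section 13.1, so a Grade 3 event can be non-serious.

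**Working it through.** The plan gives no figure to reproduce here and no calculation settles the point. The check sets the texts side by side.

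**Step 1: what each rule does, by type of event (after the last dose, before any new anticancer therapy).**

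| Event | 100-day rule | 30-day rule | Conflict? |
|---|---|---|---|
| New-onset, non-serious, judged unrelated, in the 30-day follow-up period | Recorded | Not recorded | Yes |
| New-onset, non-serious, judged attributable, in the 30-day follow-up period | Recorded | Recorded | No |
| Non-serious, after that period and up to day 100 | Recorded, any cause | Silent | No |
| Serious, to day 100 | Separate SAE rule: reported, any cause | SAEs in the 30-day period: reported, any cause | No |

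Only the first row is in conflict.

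**Step 2: does any other text break the tie?**

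- Calendar note 4 in Section 7 and Section 8.5 send the reader back to Section 13.
- The definition in Section 13.8.1 includes unrelated events. That fits the 100-day rule but does not say that it overrides the 30-day rule.
- Adverse event review at the 30-day and 100-day visits also fits the 100-day rule, again without deciding the matter.
- Sections 18.3 and 18.4 state neither an analysis window for adverse events nor whether they are tabulated by all causes or by drug-related cause.

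**Step 3: can the 30-day rule be read as an exception to the 100-day rule?** It can be carried out that way. Unrelated non-serious events would then be filtered out in the 30-day period and collected again afterwards. If the period ends at day 30, unfiltered collection runs for 100 − 30 = 70 days. If it ends with the visit window at day 37, it runs for 100 − 37 = 63 days. The protocol gives no reason for this pattern. Where Section 13.1 clearly wants a filter, before first dose, it ties the filter to its own window. The 100-day rule neither carries a filter nor mentions an exception.

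**Step 4: loose terms.** The 30-day follow-up period is not defined beyond the day 30-37 visit. The wording of the 30-day test, "new onset, non-serious adverse events should only be recorded if, in the opinion of the investigator, there is a reasonable possibility" of attribution, is not mapped to the five attribution levels in Section 13.8.4. This is why drug-related counts are described as largely, and not wholly, unaffected.

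**The case against.** The strongest reply is that a specific sentence qualifies a general one, so the 30-day rule is simply an exception and both can be followed. A related-only approach after treatment also has some support: Section 2.3 describes post-treatment follow-up in terms of drug-related toxicities and treatment-related SAEs. Part of this stands. The exception reading is workable, and the sponsor could choose a related-only rule. But the protocol does not state that choice, and the exception reading produces the unexplained gap in Step 3. The ambiguity remains.

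A reader might also draw four stronger conclusions that the documents do not support.

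- **That SAE reporting conflicts too (30 against 100 days).** The 30-day SAE sentence requires reporting of all SAEs in that period and does not say that reporting then stops. It is contained in the 100-day, any-cause rule of Sections 13.1 and 13.9.2. It is redundant, not contradictory.
- **That the loss can be sized from Table 2 (Section 3.3).** There, 256 patients had any event and "157 (51.6%) had at least one treatment related event", so (256 − 157)/256 = 99/256 = 39% had no drug-related event. That table covers serious and non-serious events from first dose to 135 days after the last dose. It includes 47 patients with malignant neoplasm progression, 42 of them Grade 5. A patient with an event on treatment is counted under either rule. The 39% therefore does not measure this window.
- **That late immune-related events would be lost.** Those recognized as possibly caused by the product are recorded under both rules. Misattribution is possible, but its extent is unknown.
- **That adverse event rates could not be pooled or compared between arms.** On-treatment and SAE counts are the same under either rule, and drug-related counts nearly so. Section 3.7 describes the arms as evaluated in parallel, Section 18.3 frames safety by regimen, and the general between-group tests in Section 18.4 do not name adverse events.

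**Conclusion.** The inconsistency is real, lies within one section, and is not resolved elsewhere. Its reach is limited to all-causality counts of new-onset, non-serious adverse events in the 30-day follow-up period. The primary endpoint and the sample size are also untouched.

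The number of events affected cannot be derived. It depends on how many unrelated, non-serious events begin in that period before any new therapy, and on which rule each site applies; the documents give neither. The conclusion assumes only that the 30-day follow-up period falls within the 100 days after the last dose, as the timing of the 30-day visit implies. The point merits correction because it governs how a secondary endpoint is recorded and omitted events are hard to recover, but it is a small one.

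**What to change.** Reconcile the two paragraphs in Section 13.1. Delete the 30-day related-only sentence, or align it with the 100-day rule, so that one instruction applies: all non-serious events are recorded, regardless of attribution, to 100 days after the last dose or the start of another anticancer therapy, whichever is first. This fits the definition in Section 13.8.1 and the reviews already scheduled at the 30-day and 100-day visits. The cut-off at new therapy already limits recording of events that belong to the next treatment.

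Keep attribution as a recorded field on the five-level scale of Section 13.8.4. Add to Section 18 that adverse events are tabulated separately for all causes and for drug-related cause, and name the window used.

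The cost is a one-paragraph edit to Section 13.1, a line in Section 18, and slightly more event entry at a visit where adverse events are already reviewed.
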